8.1.3 Electrocardiogram

Subjects have a 12-lead ECG performed as per the [Time and Events Schedule](#). ECGs performed prior to administration of study drug in the parent study (where applicable). Abnormal ECGs may be repeated at the Investigator's discretion.

8.1.3.1 Quality of Life Assessments

The 6-point Likert scale will be replaced with the KCCQ instrument ([Attachment 2](#)) and provided to subjects to completed as per the [Time and Events Schedule](#).

9. ADVERSE AND SERIOUS ADVERSE EVENTS ASSESSMENT

9.1 Definition of Adverse Events, Period of Observation, Recording of Adverse Events

An Adverse Event (AE) is any untoward medical occurrence in a clinical investigation subject administered a pharmaceutical product and that does not necessarily have a causal relationship with this treatment. An AE can therefore be any unfavorable and unintended sign (including an abnormal laboratory finding), symptom, or disease temporally associated with the use of a medicinal (investigational) product, whether or not related to the medicinal (investigational) product (ICH Guidance E2A 1994).

All AEs are collected from the time the informed consent is signed until the subject discontinues and are to be recorded on the appropriate AE pages in the eCRF and in source documents. Where possible, a diagnosis, rather than a list of symptoms, should be recorded. If a diagnosis has not been made, then each symptom should be listed individually. In addition to untoward AEs, unexpected benefits outside the investigational product indication should also be captured on the AE eCRF.

All AEs must be followed to closure (the subject's health has returned to his/her baseline status or all variables have returned to normal), an outcome is reached, stabilization (the Investigator

does not expect any further improvement or worsening of the event), or the event is otherwise explained regardless of whether the subject is still participating in the study. When appropriate, medical tests and examinations are performed so that resolution of event(s) can be documented.

9.1.1 Severity Categorization

The severity of AEs must be recorded during the course of the event including the start and stop dates for each change in severity. An event that changes in severity should be captured as a new event. Worsening of pre-treatment events, after initiation of investigational product, must be recorded as new AEs (for example, if a subject experiences mild intermittent dyspepsia prior to dosing of investigational product, but the dyspepsia becomes severe and more frequent after first dose of investigational product has been administered, a new AE of severe dyspepsia [with the appropriate date of onset] is recorded on the appropriate eCRF).

The medical assessment of severity is determined by using the following definitions:

- Mild:** A type of AE that is usually transient and may require only minimal treatment or therapeutic intervention. The event does not generally interfere with usual activities of daily living.
- Moderate:** A type of AE that is usually alleviated with specific therapeutic intervention. The event interferes with usual activities of daily living, causing discomfort but poses no significant or permanent risk of harm to the research subject.
- Severe:** A type of AE that interrupts usual activities of daily living, or significantly affects clinical status, or may require intensive therapeutic intervention.

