10.8 Safety Analyses

Adverse events will be coded using MedDRA. The number of events, incidence, and percentage of treatment-emergent adverse events (TEAE) will be calculated overall, by system organ class (SOC), and by preferred term. Treatment-emergent adverse events will be further summarized by severity and relationship to the investigational product. Adverse events related to the investigational product, AEs leading to withdrawal, SAEs, and deaths will be summarized/listed.

Clinical laboratory tests, vital signs, and ECG findings will be summarized by treatment group and visit. Potentially clinically important findings will also be summarized or listed.

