3.2 Analysis Populations

3.2.1 Safety Analysis Set (SAF)

The Safety Analysis Set (SAF) will consist of all patients who receive at least 1 dose of study drug. Patients will be analyzed according to dose received, summarized by IV dosing period, oral dosing period, and in total. The SAF will be used for the analysis of safety data.

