3.5.1 Adverse Events (AEs)

Adverse events will be coded according to the MedDRA guidance version 21.0. An adverse event is considered treatment-emergent if the start date/time of the event is:

- On or after the date/time of first IV dose for IV dosing only patients and patients who transitioned to oral dosing and were in IV period,
- On or after the date/time of first oral dose for patients who transitioned to oral dosing and were in oral period.

An overview of AEs will be provided including counts and percentages of patients with the following:

- Any TEAEs (overall and by maximum severity)
- Any study drug-related TEAEs
- Any serious TEAEs (TESAEs)
- Any TEAEs leading to discontinuation of study drug
- Any TEAEs leading to discontinuation of study.

Counts and percentages of patients will also be presented by system organ class and preferred term for each of the categories in the overview. TEAEs and TESAEs will be also provided in patient-level listings.

If an adverse event has incomplete start or stop dates, dates will be imputed to determine whether the adverse event was treatment-emergent. Details on the imputation for incomplete dates will be provided in the final SAP to correspond to CRF design and instructions. Summaries will be performed by treatment/dose group.

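### An adverse event that began on IV and drops a severity category after the switch is counted again as an oral-period TEAE, because severity changes open new records and periods are assigned by start date alone.

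*Protocol*

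**What the plan says.** **Recording.** Protocol 9.1.1 requires severity to be recorded over the course of an event, "including the start and stop dates for each change in severity", and adds: "An event that changes in severity should be captured as a new event". No direction of change is specified. The one sentence confined to worsening concerns events that existed before treatment: "Worsening of pre-treatment events, after initiation of investigational product, must be recorded as new AEs". Severity has three categories: mild, moderate and severe.

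**Assignment.** SAP 3.5.1 rests on onset alone: "An adverse event is considered treatment-emergent if the start date/time of the event is", followed by two conditions. The one for the oral period reads "On or after the date/time of first oral dose for patients who transitioned to oral dosing and were in oral period". It does not ask whether the event is new, or worse than it was at the switch.

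**Display.** Under SAP 3.2.1, results are "summarized by IV dosing period, oral dosing period, and in total". The adverse event tables in SAP 3.5.1 count patients, overall and by MedDRA class and term. Protocol 10.8 promises more: "The number of events, incidence, and percentage of treatment-emergent adverse events (TEAE) will be calculated overall".

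Neither document joins several severity records into one episode.

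**The concern.** Each rule is workable alone; the difficulty is in combining them. The recording rule turns one episode into several records, each with its own start date. The assignment rule treats each start date as an onset. The switch to oral dosing falls in the middle of follow-up, so an episode that straddles it can appear in both period columns although nothing new happened on the oral regimen.

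The result is perverse. An IV-onset event that stays at the same severity after the switch creates no oral record and is not counted in the oral column. The same event, if it gets better, is counted there.

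The incidence and severity of TEAEs is a primary endpoint (SAP 3.4.1). SAP 3.1.5 rules out hypothesis testing, so the descriptive tables are the study's main safety result. A reader will use the oral column to judge how the oral regimen is tolerated. Because oral dosing follows IV dosing, the carry-over runs from the IV period into the oral column.

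**Working it through.** The plan states no figure on this point, so there is none to reproduce. The check is a trace of the two rules, followed by the weight of one patient.

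**Step 1. Trace.** Constructed example (dates assumed): a moderate headache starts 19 days before the first oral dose, well after the first IV dose. Four courses after the switch:

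| Course | Records under Protocol 9.1.1 | Periods under SAP 3.5.1 |
|---|---|---|
| Stays moderate | one, day -19 | IV |
| Resolves with no intermediate grade | one, day -19, closed with an outcome (Protocol 9.1.3) | IV |
| Becomes mild on day +14 | moderate, day -19; mild, day +14 | IV and oral |
| Becomes severe on day +14 | moderate, day -19; severe, day +14 | IV and oral |

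The fourth row is a legitimate oral-period event. The third is the problem: the only thing that happened on oral dosing was improvement.

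**Step 2. Which cells move.**
- *Oral column, preferred-term row:* the patient is added unless already counted there for that term.
- *Oral column, any-TEAE row:* the patient is added only if there is no other oral-period TEAE.
- *Total column:* unchanged, since the patient is counted once for the term and maximum severity is still moderate.
- *Event counts:* two instead of one, but only if the number of events in Protocol 10.8 is actually reported.
- *Related and serious tables:* affected in the oral column only if the site repeats those attributes on the new record.

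**Step 3. Weight of one patient.** If k patients are counted in an oral row only for this reason and n patients received oral drug, the row is overstated by 100 × k/n percentage points. Neither document gives n. The parent study randomized 37 patients (Protocol 1.3.5), so n is at most 37 if every rollover patient came from that study. I assume the denominator is the number of patients who took oral drug.

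| n (assumed) | k = 1 | k = 2 | k = 3 |
|---|---|---|---|
| 37 | 2.7 | 5.4 | 8.1 |
| 30 | 3.3 | 6.7 | 10.0 |
| 20 | 5.0 | 10.0 | 15.0 |
| 10 | 10.0 | 20.0 | 30.0 |

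**Step 4. After a linking rule.** The third course becomes one episode, moderate at onset, counted in the IV period only. The fourth is still counted in both periods, because severity on oral dosing exceeds severity before it.

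**The case against.** **Sites may not record improvement this way.** An adverse event is by definition untoward, and Protocol 9.1.3 has an outcome category for events that are improving. A site could use that and open no new record. This stands as a reason why the frequency is uncertain. It does not remove the problem, because the sentence in 9.1.1 carries no direction and sites that follow it literally will create the record.

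**The tables count patients.** True of the SAP tables, and it fully protects the total column. It does not protect the oral column, where a patient already counted under IV is counted again.

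**Many events cannot be affected.** A mild event cannot improve by a category without resolving, and Protocol 1.3.6 describes adverse events in the parent study as generally mild. This stands and narrows the pool to events that are moderate or severe at the switch.

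**Other documents may settle it.** SAP section 5 puts programming specifications in a separate document, and SAP section 4 refers to protocol version 5.0, whereas the protocol reviewed is version 4.1. Either might contain a linking rule or a different recording rule. That cannot be checked here. The SAP should state the rule in any case, since it is where treatment-emergence is defined.

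**Stronger readings that the documents do not support.**
- *A reader might infer that events carried over from the parent study inflate the IV column in the same way.* Protocol 9.1.1 makes a new record of a pre-treatment event only when it worsens, and Protocol 9.1.4 keeps baseline conditions that do not worsen out of the eCRF.
- *A reader might take easing oedema as the typical case.* Oedema is a feature of this disease, and Protocol 9.1.4 excludes disease symptoms within their normal fluctuation, so it may not be an adverse event at all.
- *A reader might put a percentage on affected patients by assuming a number of ongoing events and a chance of severity change for each.* The documents supply neither input. Such a figure would also include worsening, which is properly counted in the oral period.

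**Conclusion.** The concern holds in limited form. Under the current wording, a non-baseline adverse event that began in the IV period and falls from severe to moderate or mild, or from moderate to mild, after the first oral dose is counted again as an oral-period TEAE. This overstates oral-period patient incidence, chiefly by preferred term.

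The total size cannot be derived from the documents. What can be said is that single patients matter: with at most 37 patients on oral drug, each one wrongly counted adds at least 2.7 points to a row. That bound assumes all rollover patients came from the named parent study. The conclusion also assumes that sites apply Protocol 9.1.1 literally and that no linking rule exists in documents outside this review. Nothing is tested, and TEAEs are also listed by patient, so a careful reader of the listings could detect the duplication. The summary tables alone would not reveal it.

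**What to change.** Add a linking rule to SAP 3.5.1:

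1. Treat records as one episode if they have the same patient and preferred term and the next start date is within one day of the previous stop date, applied after partial dates are imputed.
2. Count the episode in the period of its first onset.
3. Count it additionally in the oral period only if its severity during oral dosing exceeds its severity at the last assessment before the first oral dose.
4. Count it once in the total column.
5. Base any event counts on linked episodes.

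The cost is SAP wording and programming. Protocol 9.1.1 already requires dates for each severity change, so no new data are needed. SAP 3.5.1 leaves the imputation of partial adverse event dates to the final SAP, which is to be finalized before database lock, so the rule can go in at the same time. The small downside is a check on adjacent records, to avoid joining separate episodes or missing records closed with a gap.

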9.1.2 Relationship Categorization

A Physician/Investigator must make the assessment of relationship to investigational product for each AE. The Investigator should decide whether, in his or her medical judgment, there is a reasonable possibility that the event may have been caused by the investigational product. If there is no valid reason for suggesting a relationship, then the AE should be classified as 'not related'. Otherwise, if there is any valid reason, even if undetermined or untested, for suspecting a possible cause-and-effect relationship between the investigational product and the occurrence of the AE, then the AE should be considered 'related'. The causality assessment must be documented in the source document.

The following additional guidance may be helpful:

Term	Relationship	Definition
------	--------------	------------

Related	Yes	The temporal relationship between the event and the administration of the investigational product is compelling and/or follows a known or suspected response pattern to that product, and the event cannot be explained by the subject's medical condition, other therapies, or accident.
Not Related	No	The event can be readily explained by other factors such as the subject's underlying medical condition, concomitant therapy, or accident and no plausible temporal or biologic relationship exists between the investigational product and the event.

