9.2.6 Fatal Outcome

Any SAE that results in the subject's death (i.e., the SAE was noted as the primary cause of death) must have fatal checked as an outcome with the date of death recorded as the resolution date. For all other events ongoing at time of death that did not contribute to the subject's death, the outcome should be considered not resolved, without a resolution date recorded.

For any SAE that results in the subject's death or any ongoing events at the time of death, the action taken with the investigational product should be recorded as "dose not changed" or "not applicable" (if the subject never received investigational product).

9.2.7 Regulatory Agency, Institutional Review Board, Independent Ethics Committee, and Site Reporting

The Sponsor is responsible for notifying the relevant regulatory authorities/US central Institutional Review Boards (IRBs) of related, unexpected SAEs.

In addition, the Sponsor (or designee) is responsible for notifying active sites of all related, unexpected SAEs occurring during all interventional studies across the program.

The Investigator is responsible for notifying the local IRB, or the relevant local regulatory authority of all SAEs that occur at his or her site as required.

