5 PROGRAMMING SPECIFICATIONS

Analyses will be performed using SAS® version 9.4 or higher. All available data will be presented in patient data listings which will be sorted by patient and visit date as applicable. Detailed Programming Specifications will be provided in a separate document.

LIST OF TABLES AND LISTINGS

Number	Title	Population
Table 14.1.1	Patient Disposition	SAF
14.1.2	Protocol Deviations	SAF
14.1.3	Demographic and Baseline Characteristics	SAF
14.1.4.1	Study Drug Exposure – Intravenous	SAF
14.1.4.2	Study Drug Exposure - Oral	SAF
14.1.5	Concomitant Medications	SAF
14.3.1	Overview of Treatment-Emergent Adverse Events	SAF
14.3.2.1	Summary of Treatment-Emergent Adverse Events by System Organ Class and Preferred Term	SAF
14.3.2.2	Summary of Treatment-Emergent Adverse Events by System Organ Class, Preferred Term and Maximum Severity	SAF
14.3.2.3	Summary of Treatment-Emergent Adverse Events Related to Study Drug by System Organ Class and Preferred Term	SAF
14.3.2.4	Summary of Serious Treatment-Emergent Adverse Events by System Organ Class and Preferred Term	SAF
14.3.2.5	Summary of Treatment-Emergent Adverse Events Leading to Study Drug Discontinuation by System Organ Class and Preferred Term	SAF
14.3.2.6	Summary of Treatment-Emergent Adverse Events Leading to Study Discontinuation by System Organ Class and Preferred Term	SAF

Listing 16.2.1	Patient Disposition	All Patients
16.2.2	Protocol Deviations	All Patients
16.2.4.1	Demographic and Baseline Characteristics	All Patients
16.2.4.2	Study Drug Exposure	All Patients
16.2.4.3	Concomitant Medications	All Patients
16.2.6.1	Six-Minute Walk Test	All Patients
16.2.6.2	Patient Global Assessment (KCCQ Questionnaire)	All Patients
16.2.6.3	Physician's Assessment of Functional Class (NYHA)	All Patients
16.2.7.1	Treatment-Emergent Adverse Events	All Patients
16.2.7.2	Serious Treatment-Emergent Adverse Events	All Patients
16.2.8.1	Vital Signs	All Patients
16.2.8.2	Abnormal ECG Measurements	All Patients
16.2.8.3.1	Laboratory: Clinically Significant Chemistry	All Patients
16.2.8.3.2	Laboratory: Clinically Significant Hematology	All Patients
16.2.8.3.3	Laboratory: Clinically Significant Coagulation	All Patients
16.2.8.4	Physical Examination	All Patients

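### Protocol 9.1.2 gives two thresholds for a 'related' adverse event, so drug-related TEAEs and the sponsor's notices of related, unexpected SAEs could be under-counted

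*Protocol*

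**What the plan says.** Protocol 9.1.2 has the investigator assess each adverse event as related or not related, with no third category.

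- **Narrative, not related:** "If there is no valid reason for suggesting a relationship, then the AE should be classified as 'not related".
- **Narrative, related:** the event is related "if there is any valid reason, even if undetermined or untested, for suspecting a possible cause-and-effect relationship" between product and event. Other possible causes need not be ruled out.
- **Table, introduced by** "The following additional guidance may be helpful".
- **Table, Related row, first condition:** the timing "is compelling and/or follows a known or suspected response pattern to that product".
- **Table, Related row, second condition, which must hold as well:** "and the event cannot be explained by the subject's medical condition, other therapies, or accident".
- **Table, Not Related row:** other factors readily explain the event, and "no plausible temporal or biologic relationship exists between the investigational product and the event".

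The classification is used in three places. Protocol 10.8 summarises TEAEs by relationship. SAP 3.5.1 has an overview line for study drug-related TEAEs, and the SAP list of tables includes Table 14.3.2.3, "Summary of Treatment-Emergent Adverse Events Related to Study Drug by System Organ Class and Preferred Term". Under Protocol 9.2.7 the sponsor tells authorities, US central IRBs and active sites of SAEs that are both related and unexpected.

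**The concern.** The table is meant to help apply the rule above it, but it applies a different rule. The narrative asks whether the drug could have caused the event. The Related row asks whether anything else could explain it.

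In this population the two questions often have different answers. Protocol 1.3.6 lists cardiac failure among the most commonly reported adverse reactions to the marketed injection. The same section gives cardiac failure as an example of an event related to the disease in the parent study. Protocol 2.3 also reasons by exclusion: a high heart rate is taken as a direct drug effect when there is no evidence of worsening heart failure. An investigator used to that reasoning may find the Related row the more natural test.

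At stake are the related-TEAE summaries and one reporting duty. The study is open-label with no concurrent control, so no between-arm comparison is available to offset misattribution. Two investigators could classify the same event differently and each point to 9.1.2 in support.

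**Working it through.** The plan states no figure on this point, and none can be derived. The check sets the two rules side by side.

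**Inputs.** All come from Protocol 9.1.2. Let P mean that there is a valid or plausible reason to suspect the product, and A that another explanation exists (medical condition, other therapy or accident). I treat the narrative's valid reason and the table's plausible relationship as the same thing.

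| Case | P | A | Narrative | Table |
|---|---|---|---|---|
| 1 | yes | no | Related | Related, if timing is compelling or a known or suspected pattern is followed; otherwise neither row |
| 2 | yes | yes | Related | Neither row |
| 3 | no | yes | Not related | Not Related, if the other explanation is a ready one |
| 4 | no | no | Not related | Neither row |

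**Case 2** is the conflict. The event fails the Related row because something else can explain it. It fails the Not Related row because a plausible link exists. The form still needs one of two answers.

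**Case 1** has a smaller gap: compelling timing, or a known or suspected pattern, is a higher bar than any valid reason.

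**Case 4** shows that the table also fails to cover events with no suspected cause at all. It does not affect the related count.

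**Direction.** Anything that meets the Related row has compelling timing or fits a response pattern. Either is a valid reason, so the event is also related under the narrative. The reverse fails in case 2 and in part of case 1. The table's related events are therefore a subset of the narrative's, and using the Related row as the test can only lower the count.

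**Which outputs move.**

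- *Can fall:* the related line in the overview, Table 14.3.2.3, the Protocol 10.8 relationship summary, and the sponsor's notices under 9.2.7. SAP 3.5.1 counts patients, so a patient leaves the overview line only if every TEAE that would have been called related is reclassified.
- *Cannot move:* the SAE definition (9.2.3) disregards relationship, and 9.2.2 sends all SAEs to the safety group within 24 hours. Tables 14.3.2.1 and 14.3.2.2 (all-causality) and 14.3.2.4 (serious TEAEs) do not use the field.

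**Size.** It depends on the share of events in case 2 and on how many investigators use the Related row as their test. The documents give neither.

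**The case against.** The strongest reply is that the narrative is the operative rule. It defines both terms, covers every event and says how an event should be classified, while the table is offered only as guidance that may help. The Not Related row also bars that label where a plausible link exists, so a careful reader who finds that neither row fits would return to the narrative and record the event as related.

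Much of this stands. The table does not itself label case 2 events not related, and the harm is possible rather than certain. There is also no evidence in the documents that sites have differed. But nothing says that the narrative prevails, and an investigator who stops at the Related row has applied printed protocol text.

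Three stronger readings are tempting and are not supported:

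- *That SAE reporting is compromised.* Only the sponsor's onward notice depends on relationship. Under 9.2.7 the investigator's local duty covers all SAEs, as required. The event must also be unexpected. Protocol 1.3.6 says hypotension and cardiac failure are in the product's SPC, and 9.2.1 makes the brochure and SmPC the reference safety information, so for those events the notice would usually not change.
- *That the size can be read from the oral-study frequencies in 1.3.6.* Those are incidences by term. One patient can contribute to several, and they do not show how many events have both a drug link and another explanation. For cardiac failure (12.0% against 15.9%) and tachycardia (6.5% against 6.8%) the rate is no higher on levosimendan than on placebo.
- *That the primary endpoint is biased or the SAP hides all-causality events.* The primary endpoint in SAP 3.4.1 is incidence and severity of TEAEs whatever their cause, and the all-causality tables already come before the related one.

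**Conclusion.** The inconsistency is real and is in the current text. For an event with both a plausible drug link and another explanation, the narrative gives related and the table gives no answer. If investigators use the Related row as the test, drug-related TEAEs and the sponsor's notices of related, unexpected SAEs could be under-counted. The direction follows from the wording; the size cannot be computed.

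This rests on two assumptions: that some investigators use the table, and that 9.1.2 reads the same in the protocol in force. The protocol to hand is version 4.1, while SAP section 4 refers to v5.0. The point is worth correcting because the remedy is cheap, but it does not undermine the main safety tables.

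**What to change.** Rewrite both table rows in Protocol 9.1.2 to the narrative's threshold:

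- **Related:** there is a reasonable possibility, meaning any valid reason to suspect that the product caused the event.
- **Not related:** there is no valid reason to suspect the product.

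Delete the condition that no other explanation exists, and drop the need for a ready alternative explanation from the second row so that every event falls in exactly one category. Tell sites about the change.

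The edit will not reclassify events already assessed. For those, state in the CSR, next to Table 14.3.2.3, that the two wordings coexisted and that the related count may be low for that reason.

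The cost is a small amendment, which needs sponsor and IRB approval under Protocol 11.3.2, and a note to sites. The related-event count may become slightly less favourable to the product.
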